### **Electrocardiogram Abnormalities**

As QTc prolongation is common in ESRD patients on HD and can occur due to underlying CVC disease, haemodialysis, sodium thiosulfate, calcimimetics, electrolyte disturbances (Ca, Mg and K) and overdoses of SNF472, careful QTc assessment is essential. Any QTc interval using Bazett's formula (QTcB) >500 ms or increase >60 ms from baseline in 1 or more subjects as confirmed with consecutive ECGs will be considered abnormal. It will be reported as an AE if the investigator considers it clinically relevant. Investigators should use their discretion to monitor the subject, apply appropriate management and observe until the QTcB has decreased. At the discretion of the investigator, patients with persistent QTc prolongation may be withdrawn from the trial.

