9.3.3 ECG, Physical examination and Body weight

Electrocardiograms are collected at Screening, Week 1 (pre-dose and end of infusion), Week 6 (pre-dose and end of infusion), Week 12 (pre-dose and end of infusion) and Follow-up. The following variables are collected: RR interval, PRT axis, PR interval, QRS complex, QT interval, QTcB, QTcF, Heart rate and ECG Assessment, including clinical evaluation.

Differences in absolute change from the pre-dose to post-dose within the same visit, and the differences in absolute change from Week 1 day 1 pre-dose to all the following pre-dose measurements will be summarized (Shell T-7).

Following the recommendation of the guidance ICH E14, the following additional analyses on QTc for both Bazett's and Fridericia's formulas will be done:

- number of subjects with QTc interval > 450 ms
- number of subjects with QTc interval > 480 ms
- number of subjects with QTc interval > 500 ms
- number of subjects with QTc interval increases from predose > 30 ms
- number of subjects with QTc interval increases from predose > 60 ms

The previous parameters will be measured at any point during the study after the first drug infusion (Shell T-4). In addition, the same parameters will be summarized by visits Week 1 day 1, Week 6 day 1 and Week 12 day 5 for pre-dose and post-dose time-points (Shell T-6). The tables will be also presented for QT.

Shift tables on the ECG clinical assessment will be produced to present:

- Change from baseline on the pre-dose assessments to Week 6 and Week 12 (Shell T-9)
- Change from pre-dose to post-dose within infusion days at weeks 1, 6 and 12 (Shell T-10)

RR, QTcB and QTcF will be re-calculated using the following formulas, if it is possible:

$$RR = \frac{60}{HR}$$

$$\text{Bazzet: } QT_{cB} = \frac{QT}{\sqrt{RR}}$$
$$\text{Fredericia: } QT_{cF} = \frac{QT}{\sqrt[3]{RR}}$$

Physical examination was collected at Screening and Follow up Visit and it will be summarized and listed by subject, time-point and body system including the following information: parameter, assessment and clinical significance (Shell T-6).

Body weight was collected at Screening, Week 6 and Follow up Visit and it will be listed by subject and time-point including the following information: date, weight without shoes, Height without shoes and BMI.

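### The any-time counts of QTc above 450, 480 and 500 ms in SAP 9.3.3 mix prolongation present before dosing with prolongation that is new

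*SAP*

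**What the plan says.** SAP 9.3.3 lists five QTc counts for both Bazett's and Fridericia's corrections. Three use absolute limits, the first being "number of subjects with QTc interval > 450 ms", followed by 480 and 500 ms. Two use increases, above 30 ms and above 60 ms, the latter worded "number of subjects with QTc interval increases from predose > 60 ms". For all five, "The previous parameters will be measured at any point during the study after the first drug infusion".

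A separate by-visit table is planned, in which "the same parameters will be summarized by visits Week 1 day 1, Week 6 day 1 and Week 12 day 5 for pre-dose and post-dose". The section also summarises change from pre-dose to post-dose within a visit, and change from Week 1 Day 1 pre-dose to later pre-dose readings. On shifts it says "Shift tables on the ECG clinical assessment will be produced to present" changes from baseline and within infusion days, so those tables use the clinical reading and not QTc categories.

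Protocol 7.1.4 (Electrocardiogram Abnormalities) opens with "As QTc prolongation is common in ESRD patients on HD" and names several causes other than the study drug. Protocol 2.3.2 reports QTcB prolongation in haemodialysis patients on placebo as well as on active treatment. Protocol 5.3 and 5.4 contain no QTc criterion. SAP 6.5 confirms a single arm.

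**The concern.** A patient at 490 ms before any drug, and unchanged afterwards, is counted at both 450 and 480 ms in a window that opens with the first infusion. With no control arm there is no background rate to subtract, so each patient's own pre-treatment ECG is the only reference. The three absolute-limit rows do not use it.

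The window is also wider than the reference. One Week 1 pre-dose ECG stands against up to six later ones, and one of those, at Follow-up, is taken after treatment has ended. A patient close to a limit has more chances to cross it after the first infusion than before it. What is at stake is whether these three rows can be read at all as information about SNF472.

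**Working it through.** **1. The text.** The documents state no QTc figure to reproduce. Four facts settle the counting rule:
- the absolute-limit rows carry no pre-treatment condition (SAP 9.3.3);
- patients with prolonged QTc may enter (Protocol 5.3, 5.4);
- prolongation is described as common (Protocol 7.1.4);
- no planned table cross-classifies QTc category before and after dosing.

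**2. Why by-visit totals do not resolve it.** Suppose 6 of 15 subjects exceed a limit pre-dose and 8 exceed it later. The overlap can be 0 to 6, so new cases lie between 8 − 6 = 2 and 8 − 0 = 8. This is a logical bound. The upper end would need all six to stay at or below the limit on every later ECG.

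**3. Expected counts.** Let b be the share above the limit pre-dose, k the share of those above it again later, and i the new-onset share among the rest. All three are assumed. N = 15 is an upper bound, because Protocol Table 1 restricts ECGs to equipped sites.

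Any-time count = N[bk + (1 − b)i]; new cases = N(1 − b)i.

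| b | k | i | Any-time count | New cases |
|---|---|---|---|---|
| 10% | 50% | 0 | 0.75 | 0 |
| 30% | 100% | 0 | 4.5 | 0 |
| 60% | 100% | 0 | 9.0 | 0 |
| 30% | 100% | 10% | 5.55 | 1.05 |
| 60% | 100% | 10% | 9.6 | 0.6 |

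In the last two rows the any-time count rises while the number of new cases falls.

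**4. Share of counted subjects already above the limit, with no drug effect.** Assume patient means are N(m, s_b) and each ECG adds independent N(0, s_w). There are two pre-treatment ECGs (Screening, Week 1 pre-dose) and six later ones (Week 1 end of infusion; Week 6 and Week 12, pre-dose and end of infusion; Follow-up). For limit L let F = Φ((L − patient mean)/s_w), and let A_j be the average of F^j over patients. Then:
- counted by the any-time rule = 1 − A₆;
- of those, already above on a pre-treatment ECG = (1 − A₂ − A₆ + A₈)/(1 − A₆);
- newly above on any of six, among subjects clear before treatment = (A₂ − A₈)/A₂;
- newly above at one given time-point, among the same subjects = (A₂ − A₃)/A₂.

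Central case, m = 445, s_b = 20, s_w = 15, L = 450: A₂ = 0.4427, A₃ = 0.3699, A₆ = 0.2649, A₈ = 0.2290.
- Counted: 1 − 0.2649 = 74%, against 42% above the limit on a single pre-dose ECG.
- Already above: 0.5214/0.7351 = 71%.
- New on any of six: 0.2137/0.4427 = 48%.
- New at one time-point: 0.0728/0.4427 = 16%.

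The same formulas by numerical integration over all 12 combinations of m = 430, 445, 460; s_b = 20, 25; s_w = 10, 15 give:

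| Limit | Already above: central | Already above: range | New on any of six: central | New at one time-point: central |
|---|---|---|---|---|
| 450 ms | 71% | 56% to 87% | 48% | 16% |
| 480 ms | 42% | 30% to 69% | 16% | 4% |
| 500 ms | 26% | 18% to 57% | 4% | 1% |

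The last two columns show that restricting to subjects clear before treatment does not remove the effect of six readings. Counting by single time-point largely does.

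**The case against.** The strongest reply is that the SAP already uses each patient's own reference elsewhere. The rows for increases above 30 and 60 ms do so, and stable prolongation does not enter them. Mean changes from Week 1 pre-dose and within visits are also planned. SAP 8.1 provides listings by subject and, where appropriate, by visit, and with at most 15 subjects any value above 500 ms can be traced to its pre-dose reading. Protocol 7.1.4 separately treats a confirmed QTcB above 500 ms, or a rise above 60 ms, as abnormal. The by-visit table compares single time-points evenly. The output is descriptive, and SAP 8.1 plans no inference on safety variables unless specified otherwise.

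Most of this stands, and it rules out several stronger readings. A reader might infer that the trial cannot assess QTc at all, or that a new case above 500 ms would be hidden. The increase rows, change summaries and listings do not support that. Under the central assumptions only 1.4% of patients exceed 500 ms at one pre-dose ECG, about 0.2 of 15, so there is little chronic prolongation at that limit to hide a new case. A reader might also infer that the SAP labels these counts as on-treatment events or as its main QTc result. It does neither: all five rows are called additional analyses.

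What the reply does not remove is narrower. An increase row does not show who newly crossed a limit, separate totals do not identify people, and listings leave the reader to build the missing table by hand. The table shells are not in the text available here, so their layout could not be checked. The SAP text asks for no such split.

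**Conclusion.** The point holds for the three absolute-limit rows of the any-time table and no further. Those rows mix pre-existing with new prolongation, and no other planned summary table separates the two. The rule follows from the text. Its size does not, because the documents give no QTc distribution. Under normal, independent readings with no drug effect and the stated grid, 56% to 87% of subjects counted above 450 ms would already have been above it before treatment, with 30% to 69% for 480 ms and 18% to 57% for 500 ms. These figures illustrate and do not predict. This is a modest flaw in descriptive safety output that is cheap to repair. It affects no efficacy result and no decision rule.

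**What to change.** In SAP 9.3.3 keep the present rows, labelled as any value after the first infusion. For each limit, and for QTcB and QTcF, add the number of subjects newly above it after the first infusion among those at or below it on all available pre-treatment ECGs (Screening and Week 1 Day 1 pre-dose), with that group as the denominator. Report subjects with no pre-treatment ECG separately.

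Give the same new-case count at each single time-point: Week 1 post-dose, and Week 6 and Week 12 pre-dose and post-dose. A shift table of baseline QTc category against category at each time-point would serve equally well. This part is needed because the any-of-six count still inflates new cases.

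The cost is a few extra table rows from ECGs already scheduled, and a smaller denominator. A footnote should say that a newly-above count in a single-arm trial is not evidence of a drug effect: in the central case, 48% of subjects clear before treatment would still cross 450 ms at least once with no drug effect.

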9.4 Pharmacokinetics

The PK analysis will be summarized, listed and printed for the PK analysis set.

Plasma samples collected, at Week 1 and Week 12, pre and end of infusion will be used for PK assessment. The end of the infusion is the approximate time of C_{max}.

All concentration values below the LLQ and samples with no reportable value occurring prior to dosing will be replaced by "0". For tabulation, graphical representation and calculation purposes, all samples LLQ or with no reportable value observed after the drug administration will be set to missing.

Blood samples for the quantitation by LC-MS/MS of SNF472 will be taken on 2 different days at pre-dose and at the end of the infusion time on day 1 (Week 1), and on Week 12. Infusion should be performed during 2.5 to 4 hours at constant rate. The following parameters will be calculated:

- **Actual infusion time (T_{inf})** will be calculated as the difference between the actual clock time of the end of infusion time (EOI) and the actual clock time of the start of the infusion (SOI), i.e., T_{inf} = EOI - SOI. The actual infusion time will be expressed in minutes.
- **Actual sampling time** will be calculated as the difference between the sample collection actual clock time and the clock time of dosing starts. The actual sampling times will be expressed in minutes.

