Baseline values are a (placebo pre-dose and at 12 hours, b (active treatment pre-dose) and c (active treatment at 12 hours). (mmol/L). Green line: Normal range:1.17-1.30 mmol/L. Red line: 0.5 mmol/L: possibility of tetany and potentially life-threatening

The planned doses in the protocol were 0.5, 1.5, 5, and 10 mg/kg. PK simulation based on preclinical data predicted plasma concentrations ( $C_{max}$ ; ng/mL) of 3000, 10000, 30000 and 70000 respectively. After the 1st cohort (0.5 mg/kg), the DESC (Dose Escalation Safety Committee) decided to increase the dose to be tested in the 2nd cohort (1.5 mg/kg) to 5 mg/kg. This decision was based on PK results showing much lower values than the anticipated systemic exposure of around 2500 ng/mL as predicted by the PK model (levels were below the limit of quantification of 500 ng/mL). According to new PK estimations, 5 mg/kg was expected to produce the initially expected level of exposure with 1.5 mg/kg. The  $C_{max}$  with 5 mg/kg was 11571 ng/ml, which is nearly triple the anticipated EC50. Using the PK data of the 5 mg/kg dose and the safety data after each cohort, the DESC decided to modify the following two doses to reach the target concentrations. The doses of 9 and 12.5 mg/kg produced SNF472 plasma levels of 24394 and 42207 ng/mL, respectively.

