### 6.2. Dose Rationale

The dose selected has a range of 5.6 mg SNF472/kg to 9 mg SNF472/kg depending of subject weight. This dose range was well tolerated in Phase 1 clinical trials (SNFCT2012\_03 and SNFCT2014\_03), and is selected to be the anticipated

therapeutic dose, reaching concentrations to be at the plateau of the PK/PD relationship (see SNFCT2014\_03 CSR). To adjust the dose per kilogram, subjects are divided into 4 body weight categories (see Pharmacy manual for details).

Dose levels of SNF472 from 1 to 20 mg/kg were tested in Phase 1b/2 trials (SNFCT2014\_03) for 1 week and 10 mg/kg for 1 month, without any AE/SAE related with the compound. Cmax values expected at the dose selected are not exceeding (6-fold below) the Cmax of 127,291 ng/mL, which was the NOAEL concentration determined in dog pre-clinical studies.

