8.2.4 PK Analysis Set

All subjects who receive at least 1 dose of SNF472 and for whom either of the primary PK parameters (C_{max}) can be calculated. Further analysis sets might be defined if considered appropriate to assess the sensitivity of the PK results, e.g., subjects without any major protocol deviation thought to interfere with the absorption, distribution, metabolism, and excretion of the compound to be measured.

The following table indicates the correspondence between the above defined analysis sets and the planned statistical analysis:

Planned analysis / Analysis sets	All Subjects*	Safety*	Intention to treat	Per Protocol	PK
----------------------------------	---------------	---------	--------------------	--------------	----

Disposition, Protocol Deviations and Analysis Sets	X				
Baseline and disease characteristics		X			
Previous and Concomitant medications		X			
Treatment compliance and exposure		X			
Primary endpoint			X	X	
Secondary endpoints			X		
Safety variables		X			
PK analysis					X
PD/Biomarker analysis					X
Subgroup analysis			X		
All subject listings	X				

* Includes all patients who received at least 1 dose.

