9.4.1 Pharmacokinetic Parameters

The plasma concentrations of SNF472 obtained at predose and at the end of the infusion time (EOI) will be reported. EOI corresponds to the maximum (peak) plasma concentration during the dosing interval (C_{max}), based on data from previous clinical studies. Standard pharmacokinetic parameters will not be calculated due to the lack of experimental points in the plasma concentration-time profile of SNF472.

Descriptive statistics of the pharmacokinetic parameters will be presented by visit and timepoint and will contain the following information:

-
- SNF472 dose: expressed in mg
 - T_{inf} : actual infusion time. Expressed in minutes
 - Actual sampling time: actual sampling time. Expressed in minutes
 - Pre-dose plasma levels: expressed in ng/mL or as below of the lower limit of quantification (BLQ).
 - End of infusion plasma levels (C_{max}): expressed in ng/mL

Individual data will be flagged for exclusion if actual time differs significantly from scheduled time. In those cases when the actual infusion time and actual sampling time at the end of the infusion differs significantly from the protocol time will be excluded from statistics, based on the pharmacokinetic criteria.

PK data will be listed by subject, visit and time-point. In addition, the same information listed using all time-points will be reported in a figure (Shell F-2).

On a case by case basis, it may be necessary to exclude individual infusion time values and concentration values because they are erroneous or abnormal. Any excluded data should be flagged in the individual data listings and the reason for exclusion should also be documented. If the exclusion has a meaningful impact on the overall interpretation of the results, then it should be discussed. Planned infusion and sampling times may be used as a replacement for unknown or missing actual times, based on the pharmacokinetic criteria.

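### SAP 9.4 enters a lost pre-dose PK sample as a zero concentration; at Week 12 this records an unknown as evidence of no residual drug (minor)

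*SAP*

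**What the plan says.** SAP 9.4 sets the sampling scheme: "Plasma samples collected, at Week 1 and Week 12, pre and end of infusion will be used for PK assessment". It then gives two data rules.

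- Before dosing: "All concentration values below the LLQ and samples with no reportable value occurring prior to dosing will be replaced by" zero.
- After dosing: "all samples LLQ or with no reportable value observed after the drug administration will be set to missing".

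Each rule covers two kinds of sample: those measured and found below the lower limit of quantification (LLQ), and those with no reportable value at all.

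SAP 9.4.1 states that "Descriptive statistics of the pharmacokinetic parameters will be presented by visit and timepoint" and that pre-dose plasma levels are "expressed in ng/mL or as below of the lower limit of quantification (BLQ"). It also allows erroneous or abnormal values to be excluded case by case, with flags, documented reasons, and discussion where the effect is meaningful.

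SAP 8.2.4 limits the PK set to treated subjects "for whom either of the primary PK parameters (C_{max}) can be calculated", and its table assigns the PD and biomarker analyses to that set. SAP 9.5, however, describes the PD assessment as using samples from all subjects.

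**The concern.** A result below the LLQ (BLQ) is information: the concentration is low. A sample that was lost or failed in the assay carries no information. Before dosing, the plan turns both into the number 0; after dosing, it turns both into missing. No reason is given for treating the same failure in opposite ways.

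At Week 1 Day 1 no study drug has been given, so zero is the natural value. At Week 12 pre-dose a patient has had up to 35 of the 36 planned infusions. This is the only PK sample that looks directly at residual drug after about 12 weeks, and Protocol 2.3 limits earlier haemodialysis exposure to 28 days. A lost sample here would be tabulated as confirming no carry-over, and n would include it.

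Three smaller defects go with this:

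- SAP 9.4 replaces pre-dose BLQ values by 0, while SAP 9.4.1 reports them as BLQ. The two agree only if 0 is for calculation and BLQ for display, which the SAP does not say.
- *Prior to dosing* is not defined. A Week 12 pre-dose sample precedes that day's infusion but follows earlier ones, so either rule could be applied to it.
- A patient with no usable end-of-infusion value at either visit drops out of the PD and biomarker analyses. PD aliquots (Protocol 7.3.1) and biomarker serum (Protocol 7.4) may still be valid. A patient who stops before Week 12 has only one chance of a Cmax.

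**Working it through.** The plan gives no figure for this rule, so there is none to reproduce. The effects follow directly.

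**Inputs from the documents**

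- N = 15 (Protocol 5.1).
- Expected Cmax: Protocol 6.2 says "Cmax values expected at the dose selected are not exceeding (6-fold below) the Cmax of 127,291 ng/mL", so 127,291 / 6 = 21,215 ng/mL. Healthy volunteers reached 11,571 ng/mL at 5 mg/kg and 24,394 ng/mL at 9 mg/kg (Protocol 2.3.2).
- LLQ: not given for this trial. In the Phase 1 study "levels were below the limit of quantification of 500 ng/mL".
- Terminal half-life 69 to 105 min, from technetium phytate, which the protocol calls only a possible reflection of IP6 in humans (Protocol 2.1.2).

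**Assumptions**

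- LLQ 500 ng/mL, range 50 to 1000.
- Gap of 44 h from end of infusion to the next pre-dose sample (48 h between sessions less a 4 h infusion).
- Lognormal end-of-infusion values with CV 50% or 100%.

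**1. Expected Week 12 trough**

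Residual = Cmax × 2^(−gap / half-life).

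- 69 min: 2640 / 69 = 38.3 half-lives, leaving about 6 × 10^-8 ng/mL.
- 105 min: 2640 / 105 = 25.1 half-lives, leaving about 6 × 10^-4 ng/mL.
- 240 min: 11 half-lives, leaving 10.4 ng/mL.
- Half-life needed to leave 500 ng/mL: 44 / log2(21,215 / 500) = 8.1 h.

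**2. Lost pre-dose samples coded as zero**

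With k of 15 lost, the mean is multiplied by (15 − k) / 15 if lost samples resemble the rest.

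- k = 1: mean −6.7%, n shown as 15 instead of 14.
- k = 2: mean −13.3%, n shown as 15 instead of 13.

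If every true trough were as high as 500 ng/mL, one lost sample would give 500 × 14 / 15 = 467, an error of 33 ng/mL. For a true BLQ result coded as 0, the error for that sample is below the LLQ: 500 / 21,215 = 2.4% of expected Cmax.

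**3. Two readings of the Week 12 pre-dose rule**

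Suppose 14 of 15 troughs are BLQ and one is detectable at x. If BLQ becomes 0, the mean is x / 15 with n = 15. If BLQ is deleted, the mean is x with n = 1. The same data give a fifteenfold difference, and BLQ troughs are the expected result here.

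**4. A BLQ end-of-infusion result**

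Mean with k values deleted = 21,215. Mean with them kept at s = ((15 − k) × 21,215 + k × s) / 15.

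- k = 1: 19,801 (s = 0), 19,817 (s = 250), 19,834 (s = 500). Deletion inflates the mean by 7.0% to 7.1%.
- k = 2: 15.0% to 15.4%.
- k = 0: none.

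P(value < LLQ) = Φ( ln(LLQ / Cmax) / √ln(1 + CV²) ), taking Cmax as the median.

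- LLQ 500, Cmax 21,215: about 1 × 10^-15 at CV 50%, 3 × 10^-6 at CV 100%.
- LLQ 1000, Cmax 11,571, CV 100%: 0.0016 per sample, or 1 − (1 − 0.0016)^15 = about 2.4% for at least one of 15.

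**5. Accumulation test (SAP 9.4.2)**

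It compares Cmax between visits, so troughs do not enter. A simulation with no true change (15 pairs, assumed CV 40%, no within-subject correlation, 20,000 runs) gave these false-declaration rates:

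- no BLQ: 9.8%
- one Week 12 BLQ value deleted: 9.8%
- that value kept as 0: 9.7%

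**The case against.** The best defence is that zero is very nearly the right value. The protocol reports no detectable drug 8 h after Cmax in healthy volunteers and results suggesting no accumulation in haemodialysis patients; SAP 9.4.2 expects none. Coding a true BLQ trough as 0 is ordinary practice, as is setting a lost end-of-infusion sample to missing. SAP 9.4 takes samples on two days, each before and at the end of infusion, and SAP 8.8 pairs pre-dose and post-dose values from the same day, so *prior to dosing* most naturally means that visit's pre-dose sample. A BLQ value at end of infusion would most likely signal a failed infusion or a sampling error, and SAP 9.4.1 already has a route for such values.

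Most of this stands, and it limits the size of the problem. It does not justify entering an unknown as a measurement: the expectation of no carry-over is what the Week 12 pre-dose sample checks. Lost samples are also plausible. Protocol 7.3.1 requires crushed ice and centrifugation within 30 minutes, and SAP 8.6 has sites with 1 or 2 subjects each.

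A reader might infer that the rule does bias troughs down and Cmax up. The documents do not support that as fact. Each effect needs particular samples to occur, the trough effect is a fraction of almost nothing, and deleting BLQ troughs under the less natural reading would push their mean up instead. A reader might also infer that the accumulation conclusion is at risk; the simulation shows no material effect.

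**Conclusion.** The point holds as a minor defect of specification. Coding a lost pre-dose sample as 0 is wrong at Week 12, overstates n, and is inconsistent with the rule for the same failure after dosing. The wording also needs reconciling with SAP 9.4.1 and a definition of *prior to dosing*.

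The numerical effect is probably small: one lost sample moves the mean trough by 6.7% of a value expected to be near zero. The Cmax effect, about 7% per deleted BLQ result at N=15, is conditional on an unlikely event. Dependence of PD and biomarker results on a calculable Cmax is unnecessary and does not fit SAP 9.5.

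The sizes rest on an LLQ borrowed from an earlier study, a 44 h gap, assumed CVs, and a half-life that may not be that of SNF472. The finding about lost samples rests on none of these.

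**What to change.** Amend SAP 9.4, 9.4.1 and 8.2.4 as follows.

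- Treat a sample with no reportable value as missing at every time point.
- Define *prior to dosing* as before that visit's infusion.
- Set BLQ pre-dose values to 0 for summaries, show the number and percentage BLQ by visit, and list them as BLQ, which brings 9.4 and 9.4.1 into line.
- List and flag any BLQ end-of-infusion result and handle it under the case-by-case rule of 9.4.1, instead of deleting it automatically. Add a sensitivity summary that keeps it. The value used there hardly matters (mean 19,801 to 19,834 for one such result). Routine substitution of LLQ/2 in the main analysis is not advised: if the cause were a failed infusion or sampling error, the point would have high leverage in regressions on about 15 patients (9.4.3, 9.4.4, 9.6).
- Base the PD and biomarker analyses on treated patients with a PD or biomarker result.

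The cost is a few lines of SAP text, one programming flag and one extra summary. The only downside is that n at Week 12 pre-dose may be lower.
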